3.2. Secondary Endpoints

3.2.1. Secondary efficacy endpoints:

1. Days-alive-and-free of any episodes of acute respiratory failure through Day-28 defined by need for the following oxygen delivery resources:
 - a. High-flow nasal cannula (flow rates \geq 30L/min with $\text{FiO}_2 \geq 0.4$)
 - b. Noninvasive positive-pressure ventilation through nasal or face mask, or nasal plugs
 - c. Endotracheal intubation and mechanical ventilation
 - d. Extracorporeal membrane oxygenation
2. Mean change in the ordinal scale from baseline to Days 14 and 28.
3. Ordinal scale value on Day 14.
4. All-cause mortality through Days 28 and 60.
5. Proportion of participants alive-and-free of any episode of acute respiratory failure through Day 28.
6. Days-alive-and-free of invasive mechanical ventilation through Day 28.
7. Proportion of participants alive-and-free of invasive mechanical ventilation through Day 28.
8. Proportion of participants alive and discharged from the hospital through Day 28.
9. Proportion of participants who begin corticosteroid therapy for worsening COVID-19 illness after randomization.

3.2.2. Secondary safety endpoints:

1. Safety of IC14 as measured by change from baseline in liver (alanine transaminase, aspartate transaminase, total bilirubin), renal (creatinine), hematological (hemoglobin, white blood cell count with differential), and coagulation function (platelets, prothrombin time) through Day 28.
2. Cumulative incidence of Grade 3 and 4 clinical and/or laboratory adverse events through Day 28.
3. Cumulative incidence of serious adverse events through Day 60.

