- Record variables for Sequential Organ Failure Assessment score (SOFA; Appendix A).
- Draw the following labs if not collected as part of clinical care (values closest to 8:00 am on study day):
Complete blood count (hematocrit/hemoglobin, platelet count, white blood cell count with differential), PT/INR/PTT, Complete metabolic panel (serum sodium, bicarbonate, potassium, blood urea nitrogen, creatinine, AST, ALT, alkaline phosphatase, total bilirubin), ferritin, CRP, LDH, D-dimer. If not still hospitalized record the most recent lab values.
- Collect blood for study labs, if still hospitalized
 - Process and freeze (-80°C) plasma for prognostic biomarkers.
 - Process and freeze (-80°C) serum for PK. (40 participants)
- Collect nasal swab for viral detection.

8.3.10. Study Day 21 (if hospitalized) Conduct all study evaluations in Section 8.3.3, Daily Evaluations While Hospitalized.

- Determine and record Eight-Point Ordinal Scale performed twice daily as close as possible to 8:00 a.m and 8:00 p.m. (Appendix C).
- Record variables for Sequential Organ Failure Assessment score (SOFA; Appendix A).
- Draw the following labs if not collected as part of clinical care (values closest to 8:00 am on study day): Complete blood count (hematocrit/hemoglobin, platelet count, white blood cell count with differential), PT/INR/PTT, Complete metabolic panel (serum sodium, bicarbonate, potassium, blood urea nitrogen, creatinine, AST, ALT, alkaline phosphatase, total bilirubin), ferritin, CRP, LDH, D-dimer. If not still hospitalized record the most recent lab values.
- Collect blood for study labs, if still hospitalized
 - Process and freeze (-80°C) plasma for prognostic biomarkers

8.3.11. Study Day 28

It is preferred that this visit is in person to obtain safety laboratory tests as well as clinical outcome data. However, infection control or other restrictions may limit the ability of the participant to return to the clinic. In this case, the visit may be conducted by phone or virtually, and only clinical data will be obtained. All participants will undergo an ocular examination. This examination will be scheduled as a separate in-person visit, usually in the ophthalmology clinic. This visit should be completed at 28 +/- 1 day to obtain the Eight-Point Ordinal Scale and survival. Chest x-ray and labs should be obtained at this visit or as soon as possible after the visit.

- Record adverse events.

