3. A full ocular examination should be scheduled when the participant is clinically stable, free of COVID-19 symptoms, beyond the quarantine period, and able to comply with the exam (typically between Day 28 and before Day 60)..

4. Draw or record labs per section 8.3 at baseline and Days 2, 3, 4, 7, 14, 21, 28 if hospitalized and if not collected as part of clinical care (values closest to 8:00 am on study day. * Record Daily and Days 3 and 5 clinical lab values only if drawn as part of clinical care.

5. Whole blood samples to be drawn at selected sites on a total of 30 participants enrolled.

6. Serum PK on Days 2-4 should be drawn before study drug infusion on 40 participants.

7. Additional unscheduled sampling of anti-drug antibodies should be performed if participant has a suspected immunologically related AE.

8. Collect plasma for prognostic biomarkers.

9. Study drug will be given as a 120-min IV infusion as a single dose once daily for four consecutive days (at 24-hr intervals).

10. Remdesivir will be given as loading dose 200 mg IV on day 1 then 100 mg IV on day 2-5

11. To be assessed through examination of daily progress notes and through communication with bedside nurse and, if possible, participant

12. If still hospitalized.

13. Preferred that this visit is in person to obtain safety laboratory tests and clinical outcome data. However, if participant is unable to return to the study site clinic the visit may be conducted by phone or virtually and the chest radiograph and labs scheduled as soon as possible. If not still hospitalized and not seen in clinic, record the most recent lab values.

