13.2. Endpoints

13.2.1. Primary Endpoints

The Primary Endpoint is time to clinical recovery, defined as the time from the first dose of study drug to the first day that a participant is in categories 1, 2, or 3 on the Eight-Point Ordinal Scale through Day 28 or censored at day 28. The Eight-Point Ordinal Scale is an assessment of the clinical status on each study day. The Scale is defined as follows:

- 1) Not hospitalized, no limitations on activities

- 2) Not hospitalized, limitation on activities and/or requiring home oxygen
- 3) Hospitalized, not requiring supplemental oxygen—no longer requires ongoing medical care
- 4) Hospitalized, not requiring supplemental oxygen—requiring ongoing medical care (COVID-19-related or otherwise)
- 5) Hospitalized, requiring supplemental oxygen
- 6) Hospitalized, on non-invasive ventilation or high-flow oxygen devices
- 7) Hospitalized, on invasive mechanical ventilation or extracorporeal membrane oxygenation (ECMO)
- 8) Death

13.2.2. Secondary efficacy endpoints:

1. Days alive and free of any episodes of acute respiratory failure through Day 28 defined by need for the following oxygen delivery resource:
 - a. High-flow nasal cannula (flow rates $\geq 30\text{L/min}$ with $\text{FiO}_2 \geq 0.4$)
 - b. Noninvasive positive-pressure ventilation
 - c. Endotracheal intubation and mechanical ventilation
 - d. Extracorporeal membrane oxygenation
2. Mean change in the ordinal scale from baseline to Days 14 and 28.
3. Ordinal scale value on Day 14.
4. All-cause mortality through Days 28 and 60.
5. Proportion of participants alive and free of any episode of acute respiratory failure through Day 28.
6. Days alive and free of invasive mechanical ventilation through Day 28.
7. Proportion of participants alive and free of invasive mechanical ventilation through Day 28.
8. Proportion of participants alive and discharged from the hospital through Day 28.
9. Proportion of participants who begin corticosteroid therapy for worsening COVID-19 illness after randomization.

13.2.3. Secondary safety endpoints:

1. Safety of IC14 as measured by change from baseline in liver (alanine transaminase, aspartate transaminase, total bilirubin), renal (creatinine), hematological (hemoglobin, white blood cell count with differential), and coagulation function (platelets, prothrombin time) through Day 28.
2. Cumulative incidence of all clinical and/or laboratory adverse events through Day 28.

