13.8.4. Analyses of Safety Endpoints

Safety endpoints include continuous endpoints such as change from baseline in liver, renal, hematological, and coagulation function and binary endpoint such as adverse events. The continuous endpoints will be summarized for the treatment groups using mean \pm SD, median and interquartile range and tested using the Wilcoxon rank sum test between groups. The binary adverse event endpoints will be summarized for the treatment groups using count and proportion tested using Chi-squared test or Fisher exact test based on the number of events. The safety data analysis will be conducted at each interim analysis and reported to the DSMB.

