Based on available data regarding current standard of care with remdesivir and/or dexamethasone, sample size calculations for this study are based on a median time to recovery of 6 days in the Placebo arm and a RR ratio of 1.4. Under this scenario, enrollment of 302 study participants would be expected in order to observe 278 recoveries. Because the recovery rate in the placebo arm and the RR may vary, anticipated enrollment will be between 302-350 participants to observe at least 278 recoveries. If at least 278 recoveries are observed after 302 participants have completed the study, enrollment will stop. Otherwise enrollment will continue until 278 recoveries are observed or the maximum enrollment of 350 participants is reached. Because this study will be conducted in hospitalized patients, the dropout rate is not expected to affect these sample size assumptions in a significant manner.

14. Identification and Access to Source Data

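### Laboratory adverse events are compared as crude proportions through Day 28 although new laboratory values come mainly from in-hospital days, so a shorter stay on one arm can by itself lower that arm's count

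*Combined protocol and SAP*

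**What the plan says.** The endpoint appears in two forms. Section 3.2.2 and the synopsis have "Cumulative incidence of Grade 3 and 4 clinical and/or laboratory adverse events through Day 28"; section 13.2.3 has "Cumulative incidence of all clinical and/or laboratory adverse events through Day 28", with no grade limit. Section 13.8.4 gives the analysis: "The binary adverse event endpoints will be summarized for the treatment groups using count and proportion tested using Chi-squared test or Fisher exact test". It mentions no observation time, censoring or competing event, names no denominator, and sends the same analysis to the DSMB at each interim.

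Laboratory collection depends on hospital status:

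- Footnote 4 to Table 3: "Draw or record labs per section 8.3 at baseline and Days 2, 3, 4, 7, 14, 21, 28 if hospitalized", and also "Record Daily and Days 3 and 5 clinical lab values only if drawn as part of clinical care".
- Sections 8.3.8 to 8.3.10 (Days 7, 14, 21): "If not still hospitalized record the most recent lab values".
- Section 8.3.11 (Day 28): an in-person visit is preferred, and "Chest x-ray and labs should be obtained at this visit or as soon as possible after the visit". The visit may be remote with clinical data only, and a participant not seen in clinic has the latest earlier value recorded.
- Footnote 13 to Table 3, attached to Days 21 and 28, says that after a remote visit the labs are to be scheduled as soon as possible.

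Section 8.6 has adverse events collected by telephone after discharge. Section 13.11 plans the trial "based on a median time to recovery of 6 days in the Placebo arm and a RR ratio of 1.4".

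**The concern.** A crude proportion estimates 28-day cumulative incidence only if everyone can be seen to have the event for 28 days. A laboratory event is seen only when blood is drawn. Under section 12.3.1, a treatment-emergent laboratory event is a rise in grade, and an old value recorded again cannot show one. Recovery (categories 1-3) is largely leaving hospital, and it is the outcome IC14 is meant to speed up. Observation therefore becomes unequal in the scenario the trial is powered for, and in the direction that flatters IC14.

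This matters because section 5.1 reports low platelets in 8.3% on IC14 against 2.7% on placebo, and more serious renal failure events (5.3% against 0.9%) and serious hepatobiliary events (3.8% against 0%). Section 12.4.3.1 makes thrombocytopenia, hepatobiliary disorders and acute renal failure events of special interest. Section 12.7.3.2 has no pre-specified stopping rule other than futility, so safety rests on judgement of the reported comparisons.

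**Working it through.** **Inputs from section 13.11.** Weibull recovery time with shape 0.73, placebo median 6 days, recovery rate ratio RR = 1.4, 80% power, type I error 0.05 (taken as two-sided), 1:1 allocation.

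**Assumptions not in the documents.** Recovery ends laboratory observation (category 3 is in fact still in hospital, and deaths are ignored). Laboratory-event hazard is 1-3% per day. The share of post-discharge events caught is 0, 25% or 50%.

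**1. Reproduce the plan's model.** S(t) = exp(-λ·RR·t^0.73), with λ = ln 2 / 6^0.73 = 0.187. At Day 28 the recovered proportions are 1 - exp(-2.134) = 0.882 on placebo and 1 - exp(-1.4 × 2.134) = 0.950 on IC14, as in Table 7. Events by Schoenfeld's formula are 4(1.96 + 0.842)² / (ln 1.4)² = 278, as stated. N = 278 / 0.916 = 304 after rounding to equal arms, against 302 stated. The model is the plan's own.

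**2. Observed time.** Mean observed days are the integral of S(t) from 0 to 28.

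| Placebo median | Placebo | IC14 (RR 1.4) | Ratio |
|---|---|---|---|
| 5 days | 8.52 | 5.94 | 0.698 |
| 6 days | 9.65 | 6.90 | 0.715 |
| 7 days | 10.64 | 7.77 | 0.731 |

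At median 6 this is 34% and 25% of 28 days. With RR 1.2 the ratio is 8.11 / 9.65 = 0.84.

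**3. Observed proportion.** For a constant daily hazard h, it is the integral of h·exp(-h·t)·S(t) from 0 to 28; the true 28-day risk is 1 - exp(-28h). Median 6, RR 1.4, no capture after recovery:

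| Daily hazard h on placebo | Observed placebo | Observed IC14, equal hazard | Observed ratio | Observed IC14, hazard ratio 1.5 | Observed ratio | True 28-day risk ratio at hazard ratio 1.5 |
|---|---|---|---|---|---|---|
| 1% | 8.8% | 6.4% | 0.73 | 9.3% | 1.05 | 34.3 / 24.4 = 1.40 |
| 2% | 16.2% | 11.9% | 0.74 | 16.7% | 1.03 | 56.8 / 42.9 = 1.33 |
| 3% | 22.3% | 16.7% | 0.75 | 22.8% | 1.02 | 71.6 / 56.8 = 1.26 |

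**4. How the size moves with equal true hazards.**

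- 25% or 50% of post-discharge events caught: ratio about 0.86 or 0.93.
- Hazard decaying after dosing with time constant 3, 7 or 14 days: about 0.90, 0.84 or 0.80.
- Events confined to the first 10 days: 0.82-0.83.

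**5. An early excess.** Take a hazard ratio of 3 in the first 7 days and 1 afterwards. The cumulative hazard is (3 × 7 + 21)h = 42h, the same as 1.5 × 28h, so the true 28-day risk ratio is unchanged. At 2% per day the observed ratio is about 1.44 against a true 1.33. This early excess is not hidden.

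**6. False reassurance by significance.** With true 28-day risks of 20-50%, equal in both arms, and 151 per arm, the chance of a nominally significant difference is about 4-21% across the settings with constant hazard and 0-50% capture. The issue is mainly masking, not a spurious significant benefit.

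**7. Choice of offset.** In simulation with equal hazards, 50-80% Day 28 attendance and in-hospital events only, an offset of days to the last draw gives a rate ratio of about 0.73-0.77, because it counts the unobserved gap before the Day 28 draw. An offset of in-hospital laboratory days gives about 1.0.

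**The case against.** **Post-discharge draws are planned.** Day 28 labs are to be taken at the visit or soon after, footnote 13 asks for scheduling after a remote visit, and section 8.5 makes Day 14 and 21 visits remote only for those unable to return. This stands: zero capture is the extreme. But these passages conflict with footnote 4 and with sections 8.3.8 to 8.3.10, attendance is unknown, and one Day 28 sample cannot recover an abnormality that came and went after discharge.

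**The earlier renal and hepatobiliary signals were serious events.** This stands. Serious events are collected through Day 60 wherever the participant is, so a reader might infer that the crude analysis would hide those signals; the documents do not support that. Low platelets are described as mild to moderate, so they would mostly enter only under the section 13.2.3 wording.

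**Complete masking needs a sustained excess.** A reader might infer that a 50% excess simply vanishes. That takes a hazard ratio of 1.5 for 28 days, and the true risk ratio is then 1.26-1.40, not 1.5. IC14 is given on Days 1-4 and section 6.1.1.2 gives a half-life of 23.6 hours, so an early excess is plausible and would be much less masked. If the event hazard also falls after recovery to 25% or 10% of its in-hospital level, the distortion (observed over true ratio, equal hazards within each state, 2% per day) shrinks from 0.74 to 0.84 or 0.91.

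**Other safeguards exist.** The DSMB sees blinded safety data monthly and unblinded data twice, events of special interest are aggregated monthly, and laboratory changes from baseline are compared separately. So a claim that an excess would be concealed from the DSMB goes too far. None of these is planned to correct for unequal observation in the proportion itself.

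**Details may sit elsewhere.** The protocol refers to a separate SAP and a DSMB charter for further specifications, which are not in the documents reviewed. Taking all participants as the denominator is the natural reading of section 13.8.4, but it is not stated.

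**Conclusion.** The point holds for laboratory adverse events and for non-serious laboratory-defined events of special interest (thrombocytopenia, liver and renal laboratory changes). At the planning effect, observed time differs by a ratio of 0.715, and equal true hazards could appear as a risk ratio as low as 0.73-0.75. With partial post-discharge capture or early clustering of events, 0.80-0.93 is more likely. These figures rest on recovery as a stand-in for the end of laboratory observation and on assumed hazards and capture.

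A reader might infer that the plan favours IC14 whatever happens. It does not: with equal stay there is no differential bias, only under-ascertainment in both arms, and if IC14 lengthened stay the bias would run against it. The point is worth acting on because the distortion arises in the scenario the trial hopes for and the remedy uses data already collected.

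**What to change.** Keep the crude proportions and add to section 13.8.4, and to the unblinded DSMB reports:

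- Laboratory adverse events per in-hospital day under laboratory observation, counted to first event, discharge or death, by a Poisson model with log of those days as offset, adjusted for study-day interval (1-4, 5-7, 8-14, 15-28). Do not use days to the last draw as the offset.
- Any Day 28 outpatient draw shown separately, and carried-forward values excluded.
- A table by arm of laboratory-observed days and Day 28 laboratory attendance.
- The denominator for the crude proportions, stated.

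Reconcile the grade limit between sections 3.2.2 and 13.2.3, and the laboratory instructions for discharged participants between footnotes 4 and 13 and sections 8.3.8 to 8.3.11 and 8.5.

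The cost is analysis wording and table shells; no new data are needed. The downside is that participants who remain in hospital are sicker, so the per-day rate has its own selection: in a simulation where sicker participants stay longer, the null rate ratio rose to about 1.03-1.09. Present the two analyses side by side, not as strict bounds.

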13.8.5. Descriptive Analyses

Standard graphing and screening techniques will be used to detect outliers and to ensure data accuracy. Summary statistics for both numerical and categorical variables will be reported by study arms to describe the study sample. Comparability between the randomization groups will be assessed on demographic characteristics, baseline medications, and baseline clinical status using the ordinal scale.

13.8.6. Missing Data

The study is an in-hospital study, so missing data will be unusual. Every effort will be made to minimize missing follow-up data. For patients who do not return for Day 28 and Day 60 visits, vital status on Day 60 will be ascertained by telephone calls to the subject or relatives, or via death records, or by other available means. A sensitivity analyses with missing

endpoints imputed under conservative assumptions will be conducted to assess their effect. These sensitivity analyses will be specified in the SAP.

13.8.7. Subgroup Analyses

We have pre-specified the grouping variables as age (< 65 versus \geq 65), hypertension, diabetes mellitus, baseline viral load, and sCD14. To determine whether there is heterogeneity of treatment effect to warrant reporting of findings within subgroups, the interaction between the subgroup variable and treatment effect will be tested in the Cox model. Only if it is significant will we conduct a separate analysis within the subgroups. If warranted the subgroup analysis will be conducted using the same Cox model as for the primary efficacy endpoint, but with the subgroup variable removed from the model. In this case, we will be liberal when considering whether a subgroup has an interaction with the treatment. We will use the alpha level of 0.1 instead of the usual 0.05 for testing the interaction effect. The subgroup analysis will only be conducted for the primary endpoint. Details of the subgroup analyses will be included in the Statistical Analysis Plan.

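### Within-subgroup rate ratios are estimated only when the interaction test reaches p<0.1, so those that appear are exaggerated on average and consistent subgroups go unestimated

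*Combined protocol and SAP*

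**What the plan says.** Section 13.8.7 names five grouping variables: age (under 65 against 65 or over), plus "hypertension, diabetes mellitus, baseline viral load, and sCD14". The treatment-by-subgroup interaction is tested in the Cox model for each. The stated purpose of the test is "To determine whether there is heterogeneity of treatment effect to warrant reporting of findings within subgroups", and the rule that follows is "Only if it is significant will we conduct a separate analysis within the subgroups". The threshold is deliberately loose: "We will use the alpha level of 0.1 instead of the usual 0.05 for testing the interaction effect".

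Two further sentences set the scope. "The subgroup analysis will only be conducted for the primary endpoint", so there are five interaction tests in all. "Details of the subgroup analyses will be included in the Statistical Analysis Plan", but the combined document contains no further subgroup text. It states no multiplicity adjustment for these tests and plans no display of subgroup estimates that is independent of the test result.

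**The concern.** The interaction test measures how far apart the two subgroup estimates are. If it also decides whether those estimates are produced, only widely separated pairs are ever seen. Pre-specifying the variables does not prevent this, because the selection happens at the reporting step.

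Two misreadings follow. A reported pair suggests a stronger contrast between patient groups than the data support on average. An unreported variable looks as though the effect was shown to be consistent, when the test may simply have lacked power. sCD14 is one of the five variables and, according to Section 1.1, soluble CD14 is bound by the study drug, so a chance finding there would look plausible.

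**Working it through.** **Inputs from the plan.** There are five variables, a level of 0.1 per test and one endpoint (13.8.7), with 1:1 allocation (13.1). Section 13.11 bases the design on "a median time to recovery of 6 days in the Placebo arm and a RR ratio of 1.4" and states that "enrollment of 302 study participants would be expected in order to observe 278 recoveries". Table 7 gives 80% power, type I error 0.05, and 28-day recovery of 0.882 and 0.950 for this scenario.

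**Assumptions of this check.** The plan does not give the subgroup split, the correlation between the tests, or whether the 0.1 level is two-sided. I take two-sided tests, a 50:50 split of recoveries (30:70 as an alternative) and a range of correlations. I use the usual large-sample variance of 4/d for a log RR based on d recoveries.

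**1. The plan's own figure.** Schoenfeld's formula gives 4 × (1.960 + 0.842)² / (ln 1.4)² = 31.4 / 0.1132 = 277.3, which rounds up to 278 recoveries and matches. Dividing 278 by the mean recovery rate of 0.916 gives 303.5 participants, close to the stated 302.

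**2. What it takes to pass.** With 139 recoveries in each level, the SE of the log ratio of RRs is √(4/139 + 4/139) = √(8/139) = 0.240. The test passes only if the observed ratio of RRs is at least exp(1.645 × 0.240) = 1.48, or at most its inverse. At 30:70 the SE is √(4/83.4 + 4/194.6) = 0.262 and the threshold is 1.54.

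**3. Size of the exaggeration with no heterogeneity.** The mean of |Z| given |Z| > 1.645 is 2.06. The geometric mean ratio among passing pairs (larger over smaller) is exp(0.240 × 2.06) = 1.64, when the truth is 1.00. With an equal split, the two log RRs stay centred on the overall effect. A uniform true RR of 1.40 therefore appears as 1.40 × √1.64 = 1.79 and 1.40 / √1.64 = 1.09. At 30:70 the mean ratio is exp(0.262 × 2.06) = 1.72.

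**4. Exaggeration when heterogeneity is real (simulation, equal split).**

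| True ratio of RRs | Mean ratio among passing pairs |
|---|---|
| 1.25 | 1.71 |
| 1.40 | 1.76 |
| 2.00 | 2.10 |

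The bias shrinks as the true difference grows.

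**5. Chance that at least one pair passes with no heterogeneity.** For independent tests this is 1 − 0.9⁵ = 0.41. Simulating five test statistics with a common correlation gives:

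| Correlation | Chance of at least one |
|---|---|
| 0.2 | 39% |
| 0.3 | 38% |
| 0.5 | 33% |
| 0.8 | 23% |

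**6. Power at 0.1 (equal split).** For a true ratio of 1.3, ln 1.3 / 0.240 = 1.09 and power is about 29%. For 1.5, 0.405 / 0.240 = 1.69 and power is about 52%. For 2.0, 0.693 / 0.240 = 2.89 and power is about 89% (84% at 30:70).

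**The case against.** The strongest defence is that the rule is a recognised guard against over-reading subgroups. The plan names its variables in advance, limits the work to one endpoint, asks for evidence of interaction before any within-subgroup claim, and openly calls the threshold liberal. Details are left to the Statistical Analysis Plan, where a forest plot could still be specified. The primary test, its error rate and the sample size are untouched. All of that stands, and it makes this a minor point. It does not answer the selection effect: requiring an interaction before making a claim is sound, but requiring one before showing an estimate biases what is shown. The protocol sentence would also still need changing if the later plan showed everything.

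A reader might infer four stronger things that the documents do not support.

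- **That the reporting rule causes the 41%.** It comes from five unadjusted tests at 0.1 and is an upper figure under independence. Age, hypertension and diabetes may well be correlated.
- **That large differences are often missed.** Power for a two-fold ratio of RRs is about 89%. The weakness is at moderate differences.
- **That nothing is shown for the other variables.** The rule covers within-subgroup estimates. Nothing bars reporting all five interaction p-values.
- **That subgroup results will choose the population of the next trial.** Section 1.1 says only that success would support a larger trial, and does not mention subgroups there.

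**Conclusion.** The point holds as a low-severity defect in reporting. Under Section 13.8.7, every within-subgroup RR that appears has passed a significance filter. If the effect is truly uniform, a pair that passes overstates the contrast by a factor of about 1.64 on average, or about 1.72 at a 30:70 split. This rests on 278 recoveries, two-sided tests and the large-sample variance; the equal split is the milder of the two cases. The absence of a reported subgroup is weak evidence of consistency, because a moderate true difference (ratio of RRs 1.3 to 1.5) would be missed roughly half to 70% of the time.

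**What to change.** In Section 13.8.7, replace the sentence that makes within-subgroup analysis conditional on significance with:

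> The RR and 95% CI in every level of every pre-specified subgroup will be shown in one forest plot with the interaction p-value, whatever its size. All are exploratory, the p-values are unadjusted for five tests, and the 0.1 level is not used to choose what is shown.

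The opening purpose clause should be brought into line, since it also ties reporting to the test. Because the plot needs defined levels, state the cut-points for baseline viral load and sCD14 before unblinding; Section 13.8.7 gives none.

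This removes selective display and the exaggeration that comes from it. It does not reduce the chance that one of five interaction p-values falls below 0.1, which is why the unadjusted statement is needed. The cost is a short text change and one figure, with no new data and no change to the primary test. The downside is some risk that readers make too much of individual rows, which the exploratory label limits.
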